## **Section G: Sample Size/Data Analysis**

### **G1. Sample Size**

How many subjects (or specimens, or charts) will be used in this study?

Local: 335      Worldwide: 335

Please indicate why you chose the sample size proposed:

A total of 335 participants will be recruited for this study: 252 Veterans will be recruited to participate in the RCT; 40 Veterans who participated in iCBT and their family members (up to 40) will be invited to participate in the qualitative interview.

For the RCT, a total of 252 patients will be randomized across the 3 arms (95 to iCBT, 95 to sCBT, and 62 to TAU) to have 80% power to detect differences among groups in the primary outcomes. A recent meta-analysis of transdiagnostic treatment for anxiety demonstrated a medium effect size ( $g=.69$ ) on quality of life outcomes. Based on these findings, we are using a more conservative effect size of 0.50 to calculate the sample size that will need to be recruited and randomized to draw conclusions. We will use unequal randomization to the active intervention arms and to treatment as usual to reduce unnecessary recruitment. We also inflated the sample size to account for intraclass correlations among patients and for attrition and loss to follow-up in order to obtain the number that must be recruited for the study. The recruited sample size of 95 for iCBT and 95 for sCBT, assuming 20% attrition at 1 month and accounting for clustering of patients within therapists, will result in 49 patients per group for analysis. For our primary analyses, this sample size will have 80% power to detect a medium effect size of .57 using a two-group t-test with  $\alpha=.05$  two-sided significance level.

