### **G2. Data Analysis**

Provide a description of your plan for data analysis. State the types of comparisons you plan (e.g. comparison of means, comparison of proportions, regressions, analysis of variance). Which is the PRIMARY comparison/analysis? How will the analyses proposed relate to the primary purposes of your study?

For our primary analyses, we will compare changes between the iCBT, sCBT, and TAU groups at all time periods in a single regression using a hierarchical mixed-model analysis. Because the number of patients randomized to the 3 groups is not equal, we will test for unequal variances and if necessary, will account for this in our regression models. For outcomes with unequal variances, in the mixed model, we will estimate the variances separately and adjust the degrees of freedom for the unequal variances. A priori covariates will also be included in the model. A significant time-by-treatment interaction will be followed by pairwise contrasts to determine whether the active interventions differed from TAU and whether the active treatments differed from each other. We will report the p-values and adjust p-values post-hoc using multiple comparisons procedures (e.g., Bonferroni) as recommended in the literature. For secondary analyses, we will run hierarchical linear regression models for each outcome using the baseline and 1 month data and with the a priori covariates. Hierarchical logistic regression models will be used to test differences in treatment engagement across conditions.

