Statistical Methods

Specific Aim 1: Examine the effectiveness of iCBT in improving community reintegration and overall quality of life. Community reintegration will be measured using the 3 subscales of the CRIS-CAT: extent of participation, perceived limitations, and satisfaction with participation. Quality of life will be measured by the SF-12 Physical Component Summary (PCS) and Mental Component Summary (MCS) scores. Although our quantitative analyses will be intention-to-treat, we will provide information on the number of and characteristics of any participants who did not receive the treatment as allocated or who did not complete the study. We will tabulate baseline characteristics, such as age, race, gender, disease severity, comorbidities, and psychotropic medications. Based on recommendations of the CONSORT group,⁸¹ we will adjust analyses for variables we have decided *a priori* may be important to control (i.e., depression, period of service [OEF/OIF/OND, Gulf War, and other] concomitant psychotropic medication use, and the primary diagnosis stratification variable). Results from both an intent-to-treat and treatment completer analyses will be compared.

Hypothesis 1a: *iCBT and sCBT will significantly improve community reintegration and quality of life relative to TAU at 3-and 6-month follow-ups.* To compare changes between the iCBT, sCBT, and TAU groups at all time periods in a single regression, we will use a hierarchical mixed-model analysis. Because the number of patients randomized to the 3 groups is not equal, we will test for unequal variances and if necessary, will account for this in our regression models. For outcomes with unequal variances, in the mixed model, we will estimate the variances separately and adjust the degrees of freedom for the unequal variances. The model will contain terms for the intercept, treatment, time period and interaction between time and treatment. *A priori* covariates as well as the stratification variable of anxiety disorders will also be included in the model. A significant time-by-treatment interaction will be followed by pairwise contrasts to determine whether the active interventions differed from TAU and whether the active treatments differed from each other. We will report the p-values and adjust p-values post-hoc using multiple comparisons procedures (e.g., Bonferroni) as recommended in the literature.⁸²

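### Protocol G1 attaches its 80% power to the primary analyses, but its inputs describe the 1-month iCBT v sCBT comparison that G2 lists as secondary; the supplied documents show no power for G2's adjusted primary contrasts.

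*Protocol*

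**What the plan says.** **Protocol G1.** The section first sets a general aim of 80% power for differences among the three arms (95, 95 and 62) on the primary outcomes, naming no contrast, time point or adjusted alpha. On the planning effect it says "we are using a more conservative effect size of 0.50 to calculate the sample size". The worked calculation begins "The recruited sample size of 95 for iCBT and 95 for sCBT, assuming 20% attrition at 1 month", adds an allowance for clustering within therapists, and arrives at 49 per group. It concludes "For our primary analyses, this sample size will have 80% power to detect a medium effect size of .57 using a two-group t-test", at two-sided alpha 0.05.

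**Protocol G2.** The form asks which comparison or analysis is primary. The answer is "For our primary analyses, we will compare changes between the iCBT, sCBT, and TAU groups at all time periods in a single regression". Then "A significant time-by-treatment interaction will be followed by pairwise contrasts", which cover each active arm against TAU and iCBT against sCBT. P-values are to be reported and adjusted for multiple comparisons, with Bonferroni as an example. G2 continues: "For secondary analyses, we will run hierarchical linear regression models for each outcome using the baseline and 1 month data".

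**SAP.** Hypothesis 1a uses the three-arm model and predicts that "iCBT and sCBT will significantly improve community reintegration and quality of life relative to TAU at 3-and 6-month follow-ups". Hypothesis 1b is a 1-month regression confined to the iCBT and sCBT arms, with the baseline value as a covariate.

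**The concern.** G1 and G2 use the same phrase, primary analyses, for different things. In G1 it goes with two arms, one early time point and one unadjusted test. In G2 it means three arms, all time points and adjusted contrasts. The only worked power figure therefore matches what G2 calls secondary.

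What is at stake is interpretation. If an active arm does not separate from TAU at 3 or 6 months, a reader of G1 would suppose the trial had 80% power to find an effect of 0.57 there. The documents do not show that. G1 also names two effect sizes, 0.50 as the basis of the calculation and 0.57 as the detectable effect, and does not say that power at the first is below 80%.

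**Working it through.** **Inputs from G1.** 95 per active arm and 62 in TAU; 20% attrition at 1 month; 49 per active arm for analysis; effects 0.57 and 0.50; two-sided alpha 0.05; two-group t-test.

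**Implied design effect.** 95 × 0.8 = 76 per active arm, and 76/49 = 1.55. G1 gives neither the intraclass correlation nor the cluster size.

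**Formula.** Noncentral t with noncentrality δ = d / √(1/n₁ + 1/n₂) and n₁ + n₂ − 2 degrees of freedom. Power is the probability that |t| exceeds the two-sided critical value.

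**G1's own figure.** With 49 v 49 and d = 0.57, δ = 0.57 × √24.5 = 2.82, critical value 1.985, power 0.798. The stated 80% reproduces as a single unadjusted test. The effect detectable with 80% power is 0.572.

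**At G1's planning effect.** With d = 0.50, δ = 0.50 × √24.5 = 2.47 and power is 0.688. For 80% power at 0.50 the same test needs 64 per group (63.8 before rounding), against 49.

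**Applying an adjustment (illustration).** The documents do not fix the number of contrasts and give Bonferroni only as an example. I take two contrasts (alpha 0.025) and three (alpha 0.0167). For active v TAU I assume that 20% loss applies to TAU and still holds at 3 and 6 months, so TAU has 62 × 0.8 = 49.6 if unclustered, or 49.6/1.55 = 32 if it carries the same design effect.

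| Comparison | Quantity | Unadjusted | Two contrasts | Three contrasts |
|---|---|---|---|---|
| iCBT v sCBT, 49 v 49 | power at 0.57 | 80% | 71% | 65% |
| | power at 0.50 | 69% | 58% | 52% |
| | effect at 80% power | 0.57 | 0.63 | 0.66 |
| Active v TAU, 49 v 49.6 | power at 0.57 | 80% | 71% | 65% |
| | power at 0.50 | 69% | 58% | 52% |
| | effect at 80% power | 0.57 | 0.63 | 0.66 |
| Active v TAU, 49 v 32 | power at 0.57 | 70% | 59% | 53% |
| | power at 0.50 | 58% | 47% | 41% |
| | effect at 80% power | 0.65 | 0.71 | 0.75 |

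**What baseline data could recover.** If baseline enters as a covariate with correlation r to follow-up, the effective standardized effect is d/√(1 − r²). For 49 v 49.6, d = 0.57 and three contrasts:
- r = 0.3: 0.57/√0.91 = 0.598, power 70%.
- r = 0.5: 0.57/√0.75 = 0.658, power 80%.

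If the contrast is instead on change scores, the effective effect is d/√(2(1 − r)). That equals d at r = 0.5 (65%) and is smaller below it. The documents give no r.

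**The case against.** Several points on the other side have force.

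- **Primary analyses in G1 may mean analyses of the primary outcomes.** The SAP puts Hypotheses 1a and 1b under the same aim and reserves the word secondary for anxiety and depression outcomes. It does not rank 1a above 1b. This is a plausible account of how the wording arose, but G2 answers a direct question about the primary comparison with the same phrase and labels the baseline/1-month regressions secondary. The conflict remains.
- **iCBT v sCBT is also a contrast in the primary model.** That is so, but there it is subject to the multiplicity adjustment, and G1's test is unadjusted.
- **The t-test is a planning approximation.** The planned model uses baseline, repeated measures and covariates. This stands: a baseline correlation near 0.5, used as a covariate, would bring three adjusted contrasts back to about 80% in the 49 v 49.6 case. The adjusted figures show the size of the gap on G1's own method and are not the trial's power.
- **G1 cites a larger published effect, 0.69.** At that effect, active v TAU (49 v 49.6) has 87% power over two contrasts and 84% over three. G1 chose not to plan on it.
- **The SAP text refers to material described earlier that is not in it.** Absence of stated power can be asserted only for the supplied text.

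Two stronger readings are tempting. A reader might infer that the trial is underpowered for its primary analysis; without a correlation, a contrast count and later attrition, the documents cannot establish that. A reader might also infer that the TAU arm of 62 is too small, or that it is clearly adequate. Neither follows. Unadjusted power against TAU at 0.57 is 80% if TAU is unclustered and 70% if it shares the 1.55 design effect, and the documents do not say which applies.

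**Conclusion.** The point holds as a mismatch between the stated power and the analysis it is attached to. It should be fixed. G1's calculation is correct for an unadjusted iCBT v sCBT comparison at 1 month. It does not show 80% power for any adjusted contrast of G2's primary model, and in particular not for active v TAU at 3 and 6 months.

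One shortfall needs no added assumption: at the stated planning effect of 0.50, G1's own 49-per-group test has 69% power. The adjusted figures, 71% or 65% at 0.57, rest on the t-test, on Bonferroni and on an assumed two or three contrasts. Against TAU they also need 20% loss at the later visits and no clustering in TAU; with the same design effect there, power over three contrasts is 53%. They omit both the requirement of a significant interaction and any effect of baseline and repeated measures. Confidence is high on the mismatch and the 69%, and lower on how far the planned model departs from 80%.

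**What to change.** Reconcile G1 and G2 on which comparison is primary.

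- **If G2 stands:** label the 80%/0.57 figure as iCBT v sCBT at 1 month, one outcome, unadjusted two-sided 0.05. State that power at 0.50 is 69%. Restate power or the detectable effect for the primary contrasts, including each active arm v TAU at 3 and 6 months, at the adjusted alpha. Give the number of contrasts, the 3- and 6-month attrition, the clustering assumed in TAU and any baseline correlation relied on.
- **If the 1-month iCBT v sCBT comparison is meant to be primary:** correct G2 instead, and bring the SAP into line.

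The cost is protocol and SAP wording and one recalculation. The stated power may become less favourable. Restating it does not change recruitment.

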### **G2. Data Analysis**

Provide a description of your plan for data analysis. State the types of comparisons you plan (e.g. comparison of means, comparison of proportions, regressions, analysis of variance). Which is the PRIMARY comparison/analysis? How will the analyses proposed relate to the primary purposes of your study?

For our primary analyses, we will compare changes between the iCBT, sCBT, and TAU groups at all time periods in a single regression using a hierarchical mixed-model analysis. Because the number of patients randomized to the 3 groups is not equal, we will test for unequal variances and if necessary, will account for this in our regression models. For outcomes with unequal variances, in the mixed model, we will estimate the variances separately and adjust the degrees of freedom for the unequal variances. A priori covariates will also be included in the model. A significant time-by-treatment interaction will be followed by pairwise contrasts to determine whether the active interventions differed from TAU and whether the active treatments differed from each other. We will report the p-values and adjust p-values post-hoc using multiple comparisons procedures (e.g., Bonferroni) as recommended in the literature. For secondary analyses, we will run hierarchical linear regression models for each outcome using the baseline and 1 month data and with the a priori covariates. Hierarchical logistic regression models will be used to test differences in treatment engagement across conditions.

## **Section H: Potential Risks/Discomforts**

### **H1. Potential Risks/Discomforts**

Describe and assess any potential risks/discomforts; (physical, psychological, social, legal, or other) and assess the likelihood and seriousness of such risks:

The anticipated risks of participating in this study are minimal. However, as with any type of treatment for anxiety-based disorders, there is a chance that patients will not experience noticeable improvement in their anxiety symptoms; and some may find their symptoms worsen during treatment. At times, some patients may experience discomfort or embarrassment in disclosing personal information or in discussing issues typically addressed in therapy. While engaging in various cognitive and behavioral exercises, patients may experience momentary discomfort (e.g., talking about traumatic event, tensing parts of the body). Patients will be monitored closely by a trained clinician and will not be asked to engage in potentially anxiety-provoking exercises for prolonged periods of time or do more than they are willing. In the event that a patient remains distressed or upset after a therapy or evaluation session, that individual will be encouraged to speak to the therapist/interviewer or another mental healthcare professional. All patients will have access to study personnel during regular business hours and access to emergency services 24 hours a day, 7 days a week through the emergency department at their local hospital. The PI and co-I, [name], are experienced in the delivery of exposure-based treatments for anxiety disorders and will ensure that all patients are closely monitored, with their safety taking priority above the needs of the study.

## **H2. Data and safety monitoring plan**

Do the study activities impart greater than minimal risk to subjects?

No

## **H3. Coordination of information among sites for multi-site research**

Is the BCM Principal Investigator acting as the SPONSOR-INVESTIGATOR for this multi-site research?

No or Not Applicable

Is BCM the COORDINATING CENTER for this multi-site research?

No or Not Applicable

## **Section I: Potential Benefits**

Describe potential benefit(s) to be gained by the individual subject as a result of participating in the planned work.

Patients who participate in the study may experience functional and symptom improvement related to their anxiety.

Describe potential benefit(s) to society of the planned work.

Information obtained from this study will be used to make the treatment more available to other Veterans experiencing similar problems. Based on findings from this study, the next project will evaluate broader dissemination of the treatment. Thus, potentially many more Veterans may benefit from this study.

Do anticipated benefits outweigh potential risks? Discuss the risk-to-benefit ratio.

This protocol has a favorable risk-benefit ratio because CBT is an empirically validated procedure for treating anxiety-based disorders. Patients in this study have the added benefit of receiving close monitoring through regular assessment periods. Finally, the potential risks of the intervention are minimal and typically transient.

## **Section J: Consent Procedures**

### **J1. Waiver of Consent**

Will any portion of this research require a waiver of consent and authorization?

No

#### **J1a. Waiver of requirement for written documentation of Consent**

Will this research require a waiver of the requirement for written documentation of informed consent?

No

### **J2. Consent Procedures**

Who will recruit subjects for this study?

PI  
PI's staff

Describe how research population will be identified, recruitment procedures, any waiting period between informing the prospective participant and obtaining consent, steps taken to minimize the possibility of coercion or undue influence and consent procedures in detail.

Any member of the study staff may obtain consent from study participants. This study will include Veterans from all war eras recruited from Houston and surrounding areas. Veterans may be referred from their healthcare providers at the MEDVAMC, community-based outpatient clinics, or Veterans Centers. Participants may also self-refer to the study through posted advertisements in Veteran newsletters or Veteran list-serves. People who self-refer to the study will be asked to confirm Veteran status and if they are enrolled as a patient at the MEDVAMC. If they are, a study appointment will be scheduled; if they are not currently enrolled at the hospital, they will be provided with the phone number for patient enrollment and invited to contact study personnel once they have completed this process. During the study appointment, a member of the study staff will describe the study and review the informed consent form, explaining the risks and benefits of participation. Patients interested in participating in the study will sign VA Form 10-1086, Consent to Participate in VA Sponsored Research (see Section Q: Consent Form).

Veterans who participate in the weekend intervention (iCBT) will be invited to participate in an interview with study staff members to obtain their perspectives of this treatment format. From each weekend cohort, 1-2 Veterans will be randomly selected to participate in the interview. At the time of setting up an appointment for the interview, Veterans will be informed that they may bring along a family member to the interview to share their perspectives with the study team. When participants arrive for the interview, a member of the study staff will describe the purpose of the interview and review the informed consent form, explaining the risks and benefits of participation. Veterans and family members who participate in the study will each sign a separate consent form (VA Form 10-1086, Consent to Participate in VA Sponsored Research ).

Are foreign language consent forms required for this protocol?

No

### **J3. Privacy and Intrusiveness**

Will the research involve observation or intrusion in situations where the subjects would normally have an expectation of privacy?

No

### **J4. Children**

Will children be enrolled in the research?

No

### **J5. Neonates**

Will non-viable neonates or neonates of uncertain viability be involved in research?

No

### **J6. Consent Capacity - Adults who lack capacity**

Will Adult subjects who lack the capacity to give informed consent be enrolled in the research?

No

### **J7. Prisoners**

Will Prisoners be enrolled in the research?

No

## **Section K: Research Related Health Information and Confidentiality**

Will research data include identifiable subject information?

Yes

Information from health records such as diagnoses, progress notes, medications, lab or radiology findings, etc.

Yes

Specific information concerning alcohol abuse:

No

Specific information concerning drug abuse:

No

Specific information concerning sickle cell anemia:

No

Specific information concerning HIV:

No

Specific information concerning psychiatry notes:

Yes

Demographic information (name, D.O.B., age, gender, race, etc.):

Yes

Full Social Security #:

No

Partial Social Security # (Last four digits):

Yes

Billing or financial records:

No

Photographs, videotapes, and/or audiotapes of you:

Yes

Other:

No

At what institution will the physical research data be kept?

All paper forms of original data collected from this study will be stored in a locked cabinet in a secured office at the Michael E. DeBakey VA Medical Center, Houston, Texas. (MEDVAMC) (Room 6C-119) Paper data (aside from the consent and HIPAA forms) will not contain any HIPAA identifiers or other sensitive information. Each participant will be assigned a participant study number, which will be used on paper data. Paper data will not leave the MEDVAMC.

The purpose of collecting information covered under 38 U.S.C. 7332 is to conduct scientific research and no personnel involved in this study will identify, directly or indirectly, any individual patient or subject in any report of such research.

Research records, including identifiers will be destroyed 6 years after cutoff (at the end of the fiscal year) after completion of the research project, but may be retained longer if required by other federal regulations or sponsor archive requirement.

How will such physical research data be secured?

Data will be stored at the MEDVAMC in building 100. Data will be kept in a locked file cabinet in room 6C-119.

At what institution will the electronic research data be kept?

All research data in electronic form will be kept on a secure server of the MEDVAMC ([name]), which meets VA and BCM security requirements. The server is password-protected and access is limited to IT personal. During business and non-business hours, access to the server is behind locked doors.

The server is backed up automatically each night. Data will be stored in folders on the S drive (S:Research-Data/[name] lab) and only the research staff will be given permission (requiring a logon and password) to access these folders. All paper forms of data collected from this study will be stored at the MEDVAMC in Building 100 in a locked cabinet in a secured office (Room 6C-119). Paper data (aside from the consent and HIPAA forms) will not contain any HIPAA identifiers or other sensitive information. Each participant will be assigned a participant study number, which will be used on paper data. Paper data will not leave the MEDVAMC. Results that are presented for publication will be reported in aggregate form, and therefore will not contain individual identifying information.

Such electronic research data will be secured via BCM IT Services- provided secured network storage of electronic research data (Non-Portable devices only):

No

Such electronic research data will be secured via Other:

Yes, (describe below):

Yes, (describe below): Electronic data will be stored on a VA secure server under the main "Research-Data" folder on the S drive. The pathway is: S Drive: Research-Data/[name] Lab/H42354 Transdiagnostic.

Will there be anyone besides the PI, the study staff, the IRB and the sponsor, who will have access to identifiable research data?

Yes, identify the classes of the persons:

People who ensure quality from the institutions where the research is being done, federal and other regulatory agencies will have access to all of the research data.

Please describe the methods of transmission of any research data (including PHI, sensitive, and non-sensitive data) to sponsors and/or collaborators.

No PHI will be transmitted to sponsors or collaborators. De-identified transcripts of interviews will be sent via overnight mail to co-investigator, [name].

Will you obtain a Certificate of Confidentiality for this study?

No

Please further discuss any potential confidentiality issues related to this study.

Participants in the study will authorize digital audio recording of clinician administered interviews, treatment sessions, and qualitative interviews conducted during the study by signing the consent form. Audio recordings will be recorded using a microphone directly connected to a VA networked computer and the recording will be saved in a password-protected, encrypted file on the secure VA server, the S drive (S: Research-Data/[name] Lab/H42354 Transdiagnostic), that is accessible only by study staff and people who ensure quality from the institutions where the research is being done. The only individually identifiable information contained on the audio recording is the voice print. All recordings will be labeled with participant numbers.

Transcriptions of the qualitative interviews will be sent via overnight mail to [name] at [name] with a tracking number. Transcriptions will not contain sensitive information or any of the 18 HIPAA identifiers

